## Provide study objectives/aims/hypotheses

---

Our Overall Aim is to compare, in older adults with previous falls, the effects of a *personalized* tDCS intervention designed to target the left dlPFC on the dual task costs to standing and walking, and other physical and cognitive factors that are on the causal pathway to falls and important to everyday function. We will conduct a randomized, sham-controlled, double-blinded trial with assessments at baseline and post-intervention (immediate, 3-, 6-month follow-up) in 144 non-demented men and women (72 per arm) aged 65-85 years who report  $\geq 2$  non-syncopal falls within the previous year and are fearful of falling again, yet have no major neural or musculoskeletal disorders that explain their falls. The tDCS intervention will comprise 20, 20-minute sessions of tDCS over a 4-week period. Importantly, we will utilize current flow modeling from baseline structural MRIs to determine the tDCS electrode placement and stimulation parameters that optimize electrical current flow to the desired target within each participant's brain.

**Specific Aim 1:** To test, in older adult "fallers," the effects of tDCS intervention targeting the left dlPFC on the dual task costs to the control of standing and walking. Standing and walking will be assessed with and without a concurrent cognitive dual task (i.e., verbalized serial subtractions). Primary outcomes will be dual task costs to postural sway speed when standing, and gait speed when walking, as these are well-established measures of functional mobility that are associated with falls.

**Specific Aim 2:** To test, in older adult "fallers," the effects of tDCS intervention targeting the left dlPFC on metrics of physical function that have been linked to frontal executive networks and associated with fall risk. The primary outcome will be the Short Physical Performance Battery (SPPB). Secondary outcomes will include the Timed Up-and-Go (TUG) test of mobility, fear of falling, and habitual physical activity.

**2.0 Specific Aim 3:** To test, in older adult "fallers," the effects of tDCS intervention targeting the left dlPFC on cognitive functions that have been linked to frontal executive networks and associated with fall risk. The primary outcome will be executive function as measured by the Trail Making Test. Secondary outcomes will be derived from tests of processing speed, working memory and sustained attention.

In the proposed trial, participants randomized to the real intervention arm will receive tDCS personalized to their individual head and brain anatomy, with the goal of generating an average electric field of 0.25 V/m within left dlPFC. Briefly, this will be done by having each participant undergo a structural brain MRI, which will be used to define the 'left dlPFC' target. The MRI will also be used to determine, through segmentation, tissue boundaries of the scalp, skull, CSF including ventricles, gray matter and white matter. This information will then be imported into a software program called Stimweaver™ (Neuroelectrics Corp, Boston MA) that uses patented finite-element optimization algorithms to determine the electrode placement and current parameters required to achieve the aforementioned goal of stimulation.

We hypothesize that, in older adults with previous falls and over a 6-month follow-up, a personalized tDCS intervention targeting the left dlPFC, as compared to sham, will mitigate dual task costs to the control of standing and walking and enhance other metrics of both physical and cognitive function. In our previous study, described above in section 1.2, we found that the degree to which non-personalized tDCS is “on-target” correlates with dual task improvements, yet varies significantly across participants. A small subset of the cohort described in the previous section completed structural MRIs at baseline. Six of these participants then completed the non-personalized tDCS intervention designed to increase excitability of the left dlPFC. We used the *Stimweaver* framework to model the tDCS-induced electrical field within each participant’s brain. The normal component of this field (believed to facilitate neuronal excitability) within the left dlPFC correlated closely with reductions (i.e., improvements) in the dual task costs to gait speed. ***However, this normal component varied considerably across participants.*** These pilot data give us further confidence that 1) the left dlPFC is an important target for dual task performance, and 2) personalizing tDCS to each individual’s head and brain anatomy will likely maximize its effectiveness and reduce inter-subject variability.

## 3.0 Study Design

---

### Study design (e.g. double-blind, placebo-controlled, parallel design, etc.)

---

3.1 We will conduct a single site, sham-controlled, double-blinded, randomized trial of tDCS. Participants will perform baseline functional assessments, as well as a structural MRI of the brain. They will then be assigned to a four-week, 20-session intervention of either personalized tDCS or sham (i.e., control) stimulation, via permuted block randomization stratified by sex to ensure that equal numbers of women, and equal numbers of men, are randomized to each arm. The Neuroelectrics (Cambridge, MA) Starstim-8™ tDCS system will be used to deliver the intervention, which enables blinding of both participants and study staff. Follow-up functional assessments will be performed within three days of the final tDCS session and again three and six months later. Falls will be tracked throughout the entire duration of study participation using mail-in falls calendars.

### Study duration (total)

---

3.2 *e.g. from beginning to end, the estimated timeline to complete the project.*  
This is a 5 year project. We propose to complete study start up activities over the first two quarters of Year 1. Recruitment and enrollment of subjects to begin in the 3rd quarter of Year 1 and will be completed in the 2nd quarter of year 5. The study intervention, assessments, data processing and cleaning will proceed within the same timeline. Data analysis will begin in the first quarter of Year 5 and continue throughout the final grant year. Manuscript preparation and publication will occur in the final two quarters of Year 5.

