## Study duration for participants

### 3.3

---

Participants will be enrolled in the study for approximately 8 months, during which they will complete 26 total study visits.

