**List the number of study visits, including procedures/tests involved at each visit**

---

*e.g. blood test, x-rays, questionnaires. If numerous study visits and procedures are involved, include a study procedure timeline.*

Participants will be asked to complete 26 visits over 8 months. All study visits, except the MRI visit, will take place at the Clinical Research Laboratory at Hebrew Rehabilitation Center, Roslindale MA. The MRI visit, visit 2, will take place at the Beth Israel Deaconess Medical Center, in the MRI Suite, [name]. Free parking or transportation will be provided for all study visits.

**Visit 1—In-person screen and study familiarization (Up to 2.5 hours) at the Clinical Research Laboratory at Hebrew Rehabilitation Center, Roslindale, MA.** Individuals deemed potentially eligible via phone screen will complete an in-person screen. All screening assessments, other than the physical exam and the CDR scale, will be administered by trained research assistants. Individuals will read and sign an informed consent form approved by the Hebrew SeniorLife IRB. A medical history questionnaire will be complete and medications, blood pressure, height, body mass and years of education will be recorded. The SPPB and the TMT will be completed to ensure at least mild performance decrements in physical and executive

function. [name] or a trained clinician will then administer the CDR to characterize cognitive status and rule out dementia. [name] or a trained clinician will conduct a physical, neurological exam, and clinical gait assessment to rule out acute illness and overt neural or musculoskeletal causes of falls. Individuals who meet all inclusion and exclusion criteria will be enrolled. Participants will then complete the Physical Activity Scale for the Elderly to obtain self-reported levels of baseline physical activity, and the WTAR single word reading test of premorbid intellectual ability (1-minute administration time, to be used as an adjustor for changes in executive function).

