**Visits 24-26—(Up to 2.5 hours each visit)Follow-up Assessments at the Clinical Research Laboratory at Hebrew Rehabilitation Center, Roslindale, MA :** Participants will repeat the baseline assessment immediately post-intervention - Visit 24 (within 3 days following the final tDCS visit) and again at three-Visit 25, and six months - Visit 26. Trained research assistants will administer all the follow-up assessments at visits 24-26.

---

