### Publication Plan

---

11.1 We plan to dedicate Year 5 of this grant for data analyses and manuscript preparation and submit manuscripts for publication in appropriate peer-reviewed medical journals. Additionally, we will use the data within grant proposals to justify continued research in this area.

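### Does enrolling into the second quarter of Year 5 leave too little time for the 6-month visit?

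*Combined protocol and SAP*

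**What the plan says.** The calendar is in section 3.2, Study duration (total), which answers a form prompt asking for an estimate of the project's timeline. The project lasts five years, with start-up in the first two quarters of Year 1. The section then has recruitment and "enrollment of subjects to begin in the 3rd quarter of Year 1 and will be completed in the 2nd quarter of year 5". It adds: "The study intervention, assessments, data processing and cleaning will proceed within the same timeline". Analysis starts in Year 5 Q1 and continues through that year, and "Manuscript preparation and publication will occur in the final two quarters of Year 5".

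Four other places bear on it:

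- Section 3.3, Study duration for participants: "Participants will be enrolled in the study for approximately 8 months".
- Section 5.1, list of study visits: "Participants will be asked to complete 26 visits over 8 months". Under Visit 1 it says: "Individuals who meet all inclusion and exclusion criteria will be enrolled".
- Section 5.1, Visits 24-26: the baseline assessment is repeated within 3 days of the last stimulation visit "and again at three-Visit 25, and six months - Visit 26". Section 3.1, Study design, likewise counts follow-up from the last session.
- Section 11.1, Publication Plan: "We plan to dedicate Year 5 of this grant for data analyses and manuscript preparation".

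**The concern.** If a person counts as enrolled on passing the Visit 1 screen, section 3.2 seems to ask for something impossible. Entry stays open until Year 5 Q2, all assessments and cleaning share that window, and yet every participant still has about 8 months to go after entry. The last people in would be seen while manuscripts are being written, and some after the project has ended. The Publication Plan adds to the doubt, because it gives Year 5 to analysis and writing while section 3.2 may still be recruiting for half of that year. No section gives a date for the last participant's last visit.

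The 6-month visit is the one a squeezed calendar would remove first. The main hypothesis runs over a 6-month follow-up, and Aim 1 estimates differences at each time point to judge how long the effect lasts. The Sample size determination section counts on 114 evaluable participants at that visit and makes no separate allowance for administrative loss.

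**Working it through.** **Participation time.** The visits add up: 1 screening + 1 MRI + 1 baseline + 20 sessions + 3 follow-ups = 26, as stated. From the first session to the 6-month visit takes 4 weeks + 3 days + 6 months, about 7.0 months. About 1 month is left for screening, MRI and baseline, so the stated 8 months is reproduced.

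**Calendar, in elapsed project months.** Quarter k of year y runs from 12(y−1)+3(k−1) to 12(y−1)+3k. Enrolment opens at month 6, Year 5 Q2 is months 51 to 54, and the writing period is months 54 to 60. Adding 8 months to 51–54 gives 59–62. With the bare 7 months it is 58–61, so the slack in the 8-month figure does not remove the overlap.

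**Two workable readings.** Uniform accrual is an assumption.

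- *Enrolment means all participation.* Section 3.3 uses the word this way, and section 4.7 speaks of events during a participant's enrolment. Assessments then end by month 54 and last entry is by 54 − 8 = month 46. Nobody loses the 6-month visit.
- *Enrolment means entry at Visit 1.* Entry closes at month 54, visits continue until the project ends at month 60, and the assessment and writing dates move. Accrual is 144/48 = 3.0 per month. People entering after 60 − 8 = month 52 would miss the visit: 3.0 × (54 − 52) = 6. If entry closes at month 51, nobody does.

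**Power at 6 months.** Aim 1 assumes SD 20%, serial correlation 0.75, a difference of 8% and 57 per arm. SE = 20 × √(1 − 0.75²) × √(2/n per arm).

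- Plan: n = 57, SE = 2.48, power 0.898. This reproduces the stated 90%.
- Six fewer: (144 − 6) × 0.8 = 110.4, or 55.2 per arm; SE = 2.52, power 0.888.

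**Publication Plan.** It says what Year 5 is for. It does not rule out participant visits in that year, and section 3.2 also places analysis throughout Year 5 and manuscripts in its second half.

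**The case for a change.** The strongest opposing case takes section 3.2 literally on both counts: entry runs to month 54 and all visits stop then as well. Everyone entering after month 46 would lose the 6-month visit, which is 3.0 × 8 = 24 people. If they came on top of the planned 20% missingness, (144 − 24) × 0.8 = 96 would be evaluable, or 48 per arm. That gives SE 2.70 and power 0.842 at that visit. If they were instead counted inside the 20% (28.8 people), only about 5 of the other 120 could be missing for any other reason, against planned attrition of up to 15%.

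The arithmetic is right, but the premise has no support. Nothing in the documents says that follow-up is cut short on a calendar date, and sections 3.1 and 5.1 tie it to each participant's last session. Even under this reading the repeated-measures comparison over three visits would keep power of about 0.98 (0.984 falling to 0.978, assuming compound symmetry and a constant effect).

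What stands is the wording. Visit 1 does use enrolment for a single event, and on that usage section 3.2 cannot be met as written. Nothing elsewhere settles which usage was meant. Form A gives dates of access to identifiable data from 09/04/2018 to 06/30/2023, about 58 months, but the form allows these to be approximate and they are not tied to the start of Year 1.

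**Conclusion.** This is a loose sentence in an estimated project timeline. The visit schedule, the analysis model and the sample-size assumptions do not depend on it, and a team that follows the visit schedule as written gets sound results. On the two workable readings the 6-month visit loses 0 to 6 of 144 people and power stays between 0.888 and 0.898. That range assumes uniform accrual, about 8 months per person and the plan's own variance inputs. A late-calendar shortfall would fall on both arms alike, so no bias is shown, and the evaluable number and power in the Sample size determination section are not shown to be wrong.

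Closing entry at month 46 would need 144/40 = 3.6 participants per month in place of 3.0, which is 20% faster accrual. Keeping entry open longer shortens the time for analysis and writing. That is a scheduling trade-off for the study team. Stating a last-entry date and a last Visit 26 date would tidy the text at a routine amendment, but it would change no result.

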## Study duration for participants

### 3.3

---

Participants will be enrolled in the study for approximately 8 months, during which they will complete 26 total study visits.

## 4.0 Participant Selection and Withdrawal

---

### Source of study participants

#### 4.1

Participants will be recruited from the Boston area community, senior housing facilities in urban and suburban areas, research recruitment repositories including the "Mobility and Brain Function" repository, multiple clinics at the BIDMC, and advertisements within regional media outlets and website posting (IFAR and clinicaltrials.gov )

### Total target number of participants to be enrolled

#### 4.2

*If you are enrolling from multiple sites or cohorts, list the total target number per site and/or cohort.*

We will enroll 144 individuals aged 65-85 for this study.

### Inclusion criteria

---

Our target population will be older men and women who are vulnerable to future falls, as defined by a recent history of recurrent falls *and* fear of falling again in the future, yet who do not suffer from dementia or other major neurological, musculoskeletal or cardio-respiratory disease. We will also ensure that participants have at least mild physical and executive performance decrements, such they have room to improve on related assessments, but are not so impaired that they cannot participate nor benefit from the intervention.

#### Inclusion criteria:

#### 4.3

1. Aged 65-85 years.
2. Self-report of two or more falls within the past year. Falls will be defined by any event in which the individual unintentionally comes to rest on the ground or other lower level, not as a result of a major intrinsic event (e.g., syncope) or an overwhelmingly external hazard (i.e., car accident).
3. Self-report of fear of falling, as defined by a "yes" answer to the yes-or-no question "Are you worried that you will fall in the future?"
4. At least some mild performance decrement in physical *and* executive function as defined by A) a score of nine or below on the SPPB (range=0-12, 12 reflecting best

performance), and B) a score below the 75% of performance based upon age- and education-based norms in the Trail Making Test (TMT, part B).

## Exclusion criteria

---

Exclusion Criteria have been selected to ensure safety and optimize compliance, while minimizing confounds due to overt disease or conditions that may significantly influence study outcomes:

4.4

***Exclusions based upon phone screening:*** Self report of 1) inability to stand or walk unassisted for 60 sec, 2) hospitalization within the past three months due to acute illness, or as the result of a musculoskeletal injury significantly affecting gait or balance (to minimize confounding due to recent fall-related injuries), 3) unstable medical condition, 4) a diagnosis of a gait disorder, Parkinson's disease, Alzheimer's disease or dementia, multiple sclerosis, previous stroke or other neurodegenerative disorder, 5) chronic vertigo, 6) myocardial infarction within the past 6 months, 7) active cancer for which chemo-/radiation therapy is being received, 8) psychiatric co-morbidity including major depressive disorder, schizophrenia or psychosis, , 9) chronic use of any sedating medications (sedatives, anti-psychotics, hypnotics, anti-depressants), or change in medication within the previous month, 10) legal blindness, or 11) contraindications to MRI or tDCS, as recorded on a standardized screening questionnaire, which include a reported seizure within the past two years, use of neuro-active drugs, the risk of metal objects anywhere in the body, self-reported presence of specific implanted medical devices (e.g., deep brain stimulator, medication infusion pump, cochlear implant, pacemaker, etc.), or the presence of any active dermatological condition, such as eczema, on the scalp. Potentially eligible individuals will then complete the Telephone Interview of Cognitive Status (TICS). We will exclude those with marked dementia (score<22) to reduce likelihood of in-person exclusions due to dementia (see below).

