## 7.1

**TRANSCRANIAL DIRECT CURRENT STIMULATION (tDCS):** tDCS has been widely used during the last decade demonstrating non-significant risk to participants. Expected side effects include:

1) Sensations reported by subjects under the electrodes: (These sensations can sometimes continue throughout and for a brief period following completion of the tDCS but usually resolve shortly after the initiation of tDCS)

- Mild tingling (20-70%)
- Light itching (30-40%)
- Slight burning (10-22%)
- Discomfort or mild pain (10-18%)

2) Other effects that can occur both during and after tDCS include:

- Mild fatigue (15%)
- Skin redness (20%)
- Headache (10-15%)
- Difficulties in concentration (11%)

3) Additionally the following rare side effects have been described:

- Nausea (<(<1%)

- Nervousness (<1%)
- Although it has never been reported in tDCS, seizures are a theoretical risk. Individuals with a history of seizures and/or a diagnosis of epilepsy will therefore be excluded from this study.

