## **Potential psychosocial (non-medical) risks, discomforts, inconveniences of study procedures**

---

TESTS OF MENTAL FUNCTION: Risks associated with answering these cognitive test questions are minimal, but participants may experience mental fatigue and/or anxiety during this form of testing.

INCONVENIENCES: We will minimize the risk to subjects in this study by excluding those with conditions listed in the exclusion criteria. The proposed protocol requires multiple visits and therefore considerable participant burden with respect to time and effort. Our study team has a strong track record of successful clinical research requiring similar participation, and retention has been high in these projects. The Clinical Research Laboratory at IFAR is located next to a cafeteria and equipped with comfortable seating, a TV, movies, books and magazines to keep individuals occupied during resting periods. Several additional strategies will be employed to minimize participant burden and maximize adherence to the protocol. We will:

7.2

- Develop a personal relationship between participants and members of the staff by matching research assistants with individual participants.
- Schedule appointments at convenient times with familiar staff.
- Explain to participants all aspects of their participation and follow up. We will demonstrate and practice study procedures before beginning data collection.
- Provide reminders of all appointments and follow-up phone calls.
- Include personal notes in the participant's data file to remember events in the life of the participant; these can be commented on at the next visit (e.g., birthday, birth of a grandchild).
- Provide snacks during all visits.
- Provide transportation for all visits, if required
- Provide valet or dedicated, on-site parking spaces.
- Compensate participants for visits.

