## 2.5

3) Additionally the following rare side effects have been described:

- Nausea (<(<1%)
- Nervousness (<1%)

4) Although it has never been reported in tDCS, seizures are a theoretical risk. Individuals with a history of seizures and/or a diagnosis of epilepsy will therefore be excluded from this study.

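### The exclusion criteria apply a two-year seizure window and do not name epilepsy, while the two tDCS risk statements exclude any seizure history or epilepsy diagnosis

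*Combined protocol and SAP*

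**What the plan says.** Item 11 of the phone-screening exclusions in section 4.4 covers "contraindications to MRI or tDCS, as recorded on a standardized screening questionnaire", and continues "which include a reported seizure within the past two years, use of neuro-active drugs". The seizure entry carries a two-year limit, and epilepsy is not mentioned. The neurological diagnoses in item 4 of the same list end with "multiple sclerosis, previous stroke or other neurodegenerative disorder", and epilepsy is not among them. The in-person exclusions that follow concern dementia and gait disorders only.

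Section 7.1 (Potential medical risks of study procedures), under tDCS, says that "seizures are a theoretical risk. Individuals with a history of seizures and/or a diagnosis of epilepsy will therefore be excluded from this study". The Starstim device form repeats the commitment in its section 2.5: "Individuals with a history of seizures and/or a diagnosis of epilepsy will therefore be excluded from this study". Neither statement has a time window, and both name epilepsy.

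On how eligibility is applied, the Visit 1 description in section 5.1 says "Individuals who meet all inclusion and exclusion criteria will be enrolled", and section 7.2 says "We will minimize the risk to subjects in this study by excluding those with conditions listed in the exclusion criteria".

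**The concern.** The two risk statements present the seizure exclusion as the safeguard against the theoretical seizure risk they name. That safeguard is not in the list of criteria in the form in which the IRB was told of it. A person can pass section 4.4 and still be someone whom sections 7.1 and 2.5 say will not be in the trial. Staff who work from section 4.4 as printed could enrol that person and, if the allocation is active, give up to 20 sessions of stimulation. The participant would then have been enrolled contrary to the risk statement on which the IRB relied, whether or not any harm followed.

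**Working it through.** The plan states no figure on this point. The check is a comparison of texts, followed by a conditional estimate of size.

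**The rules side by side**

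| Person (taking no neuro-active drug) | Section 4.4, item 11 | Section 7.1 and Starstim form 2.5 |
|---|---|---|
| Seizure within two years | Excluded | Excluded |
| Last seizure more than two years ago, no epilepsy diagnosis | Not excluded by the seizure wording | Excluded |
| Epilepsy diagnosis, no seizure in two years | Not named | Excluded |

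Most people with medicated epilepsy are probably caught by the neuro-active drug entry in item 11, so the conflict is confined to rows two and three.

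**Whether another provision settles rows two and three**

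- Item 4 of section 4.4 lists gait disorder, Parkinson's disease, dementia, multiple sclerosis, stroke and neurodegenerative disorders. Epilepsy is not listed.
- The in-person exclusions cover dementia by CDR and gait disorders.
- The introduction to the inclusion criteria (section 4.3) describes a population free of other major neurological disease. That is general wording. It might be read to cover diagnosed epilepsy, but it does not settle a single remote seizure.
- The Visit 1 clinician assessment is a "physical, neurological exam, and clinical gait assessment to rule out acute illness and overt neural or musculoskeletal causes of falls". A remote seizure is a matter of history and lies outside those purposes.
- Visit 1 also includes a medical history questionnaire and a record of medications. These could bring a seizure history to light, but the protocol attaches no seizure rule to them.

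None of these resolves the conflict.

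**Size, conditional on an assumption**

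Let p be the share of otherwise eligible people in rows two and three. The documents do not give p. I take 0.001 to 0.01 as an assumption, and suppose that no other screening step catches anyone.

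- Enrolled, n = 144 (section 4.2): 144 × 0.001 = 0.14 and 144 × 0.01 = 1.44 people expected.
- Active arm, n = 72 (section 2.0): 72 × 0.001 = 0.07 and 72 × 0.01 = 0.72 people expected.
- Chance of at least one among 144, 1 − (1 − p)^144: 1 − 0.999^144 = 0.134 and 1 − 0.99^144 = 0.765.
- Phone screens, about 1,500 (the request for access to health information): 1,500 × 0.001 = 1.5 and 1,500 × 0.01 = 15 people. This is a ceiling on those newly ineligible under the broader rule, because some would fail another criterion anyway.

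**The case against.** The strongest reply is that item 11 is not a closed list. Its examples are introduced as inclusions, the operative test is a standardised questionnaire, and sections 7.1 and 2.5 belong to the same application. Read together, the broader rule could govern and nobody would be wrongly enrolled. The phone-screen and eligibility questionnaires are listed in section 5.6 but are not reproduced, so the wording staff use cannot be checked. The history questionnaire and medication review at Visit 1 give a second chance to detect a seizure history. The sentence in section 7.2 is a general one under the heading of inconveniences and does not say that section 4.4 is the only source of exclusions. The prevalence range is assumed. The protocol says a seizure has never been reported with tDCS, and it caps current at 2.0 mA per electrode and 4 mA in total.

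Much of this stands as a limit on the consequence. It is not known that anyone would be wrongly enrolled, and the size estimate carries no evidential weight. It does not remove the inconsistency. An open-ended list leaves room for further contraindications, but it does not naturally widen an entry that states its own limit; giving two years implies that older seizures are acceptable. If the questionnaire asks about any seizure, section 4.4 is wrong. If it asks about two years, sections 7.1 and 2.5 are wrong. Something needs correcting in either case.

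**Conclusion.** The concern holds. The protocol gives two incompatible seizure rules, and the narrower one is in the list of exclusion criteria. This conclusion rests on the text alone and does not depend on the assumed prevalence. The number affected is probably very small and may be zero: about 0.1 to 1.4 enrolled participants, with a 13% to 76% chance of at least one, if the share is 0.1% to 1% and no other screening step intervenes. The width of that range reflects the tenfold width of the assumption. Primary outcomes, randomisation, analysis, sample size and power are unaffected. It should be fixed because it concerns a safety criterion on which the IRB was given a specific assurance, and because the correction is easy.

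**What to change.** In section 4.4, item 11, replace the two-year seizure entry with one that excludes any history of seizures or a diagnosis of epilepsy, so that it agrees with section 7.1 and with section 2.5 of the Starstim form. Check that the phone-screen questionnaire, the eligibility questionnaire and the consent form say the same. If the investigators do intend the two-year window, leave item 11 as it is, correct sections 7.1 and 2.5 to state it, and tell the IRB.

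The cost is a one-sentence amendment and a check of three forms. Under the broader rule, and on the assumption used above, at most about 2 to 15 of the roughly 1,500 people phone-screened would become ineligible on this item. The target of 144 and the power figures stay as they are.
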